9.7 Data Management

The Principal Investigator will be responsible for overseeing entry of data into an in-house password protected electronic system and ensuring data accuracy, consistency and timeliness. The Principal Investigator, associate investigators, Hematology Branch fellows, research nurses and/or a contracted data manager will assist with the data management efforts. Data will be abstracted from Clinical Center progress notes as well as from progress notes forwarded from home physician. Laboratory data from NIH will be imported electronically from CRIS into an in-house clinical trial database. Laboratory values from referring home physicians will be entered into the system. Identifiable data will not be sent outside of the NIH without IRB approval and an executed agreement.

All human subjects personally identifiable information (PII) will be recorded according to the NIH policy. Primary data obtained during the conduct of the protocol will be kept in secure network drives or in approved alternative sites that comply with NIH security standards. Primary and final analyzed data will have identifiers so that research data can be attributed to an individual human subject participant, e.g., unique code, or minimum PII required for subject identification. Study data will be housed in the Hematology Branch P Drive, a secure limited access drive.

Novartis will receive quarterly accrual and toxicity information as detailed in the CRADA. In order to maintain subject confidentiality, all communications relating to the study will identify participants by assigned subject study numbers. No personally identifiable information will be sent to Novartis. In accordance with local and federal regulations, the Investigator will allow Novartis personnel or their designee, access to all pertinent medical records in order to verify the data gathered and to audit the data collection process.

The US Food and Drug Administration (FDA) may also request access to all study records, including source documentation for inspection.

End of study procedures: Data will be stored in locked cabinets and in a password protected database until it is no longer of scientific value.

Loss or destruction of data: Should we become aware that a major breech in our plan to protect subject confidentiality and trial data has occurred, the IRB will be notified.

10. DATA AND SAFETY MONITORING

10.1 Safety Monitoring

Principal Investigator: Accrual, efficacy and safety data will be monitored by the Principal Investigator, [name].

NIH Intramural IRB: Prior to implementation of this study, the protocol and the proposed patient consent and assent forms will be reviewed and approved by the properly constituted Institutional Review Board (IRB) operating according to Title 45 CFR 46. This committee will also approve all amendments to the protocol or informed consent, and conduct continuing annual review so long as the protocol is open to accrual, in follow up of subjects or in data analysis.

NHLBI DSMB: The NHLBI Data Safety and Monitoring Board will review the protocol at 6 to 12 month intervals. A progress report will be forwarded to the DSMB at these times and their recommendations will be expeditiously implemented. The DSMB may recommend early termination of the study for considerations of safety and efficacy.

FDA: An annual progress report, any amendments to the protocol, and any change in the status of the protocol will be forwarded to the FDA:

CDER Therapeutic Biological Products Document Room
Center for Drug Evaluation and Research, Food and Drug Administration
[name]
[contact]

Novartis: An annual progress report, any amendments to the protocol, and any change in the status of the protocol will be forwarded to:

[name]
Clinical Research Manager
Novartis Pharmaceuticals Corporation
[name]
[name]
USA
[contact]
[contact]
[contact]
[contact]

10.2 Event Characterization and Reporting

Events include Adverse Events (AE), Serious Adverse Events (SAE), Protocol Deviations (PD), Unanticipated Problems (UP), and non-compliance. The characterization (e.g., seriousness, expectedness, etc.) of the event will determine the reporting requirements.

The principal investigator will review all events (AEs, PDs, UPs, SAEs) to determine the seriousness, expectedness, and reportability of the event. As required and/or needed, the principal investigator will review the events with the Sponsor to make the final determination of seriousness and reportability.

10.2.1 Assessment of Safety

Definitions

Please refer to Policy 801 “Reporting Research Events” for current definitions.

10.2.2 Protocol Deviation (PD) Characterization

It is anticipated that approximately 50% of the clinical monitoring laboratory testing performed during the first 6 months will not be performed within +/- 3 days of the required time points, with the exception of the month 3 and 6 landmark visits. If the clinical laboratory monitoring occurs outside the +/- 3 day window, these events will be captured in the database. If the number of events per subject or per cumulative enrolled subjects exceeds 50%, which is a frequency greater than what is expected, this will be reported at time of continuing review. Please note, subjects and providers are reminded of the importance of the timely

completion of the clinical laboratory testing.

Questionnaires that are not completed at the required time point due to clinical status (e.g. critically ill), will be recorded in the database.

Interruptions in eltrombopag dosing that are clinically indicated per section 5.3, will be recorded in the medical record.

In addition, CsA interruptions, such as delay in request for medication refills or medication errors by subjects, will be recorded in the medical record.

10.2.3 Adverse Events (AEs) Characterization

Non-hematologic abnormal laboratory findings used to evaluate the safety of this protocol regimen will include any change from laboratory assessments done prior to first dose of study medication that result in a progression to a grade 3 or 4 laboratory toxicity or are characterized by any of the following:

- Results in discontinuation from the study
- Is associated with clinical signs or symptoms
- Requires treatment or any other therapeutic intervention
- Is associated with death or another serious adverse event, including hospitalization
- Is judged by the Investigator to be of significant clinical impact
- If any abnormal laboratory result is considered clinically significant, the investigator will provide details about the action taken with respect to the test drug and about the patient's outcome.

The AEs will be attributed (unrelated, unlikely, possibly, probably or definitely related) to study medication and/or disease. The AEs will be graded by severity utilizing CTCAE version 4.0.

Duration of adverse event collection: The collection and recording of events in the database will begin on the first day of initiation of the study drug and will continue for 30 days after the 6 month landmark visit or for 30 days after treatment is discontinued if before the 6 month landmark visit, after which the events will be captured in the medical record but not abstracted or recorded in the database or toxicity tables.

AEs that are captured in the database will be followed until satisfactory resolution as long as the subject remains on study.

Exclusions to AE data capturing:

- In view of the underlying illness, severe aplastic anemia all patients will enter the study with abnormally low blood counts that would meet criteria as grade 3 or more commonly grade 4 toxicity, and requiring frequent platelet and/or red cell transfusions, and thus AEs regarding hematologic lab values including thrombocytopenia or platelet-transfusion dependence, anemia or red cell transfusion dependence, neutropenia, lymphopenia, or leukopenia will not be captured in the research database. Thus, we will collect hematologic laboratory values in the subject's source documents, but will not record or report these abnormalities as adverse events in the research database.
- In addition, the following non-hematologic AEs will be captured only in the source documents and will not be recorded in the database:
 - Because CsA, h-ATG (ATGAM®) and eltrombopag (Promacta®) are FDA approved drugs with known toxicity profiles, any observed or volunteered adverse events that are listed on the package insert will not be captured in the research database unless (1) the adverse event is more severe or occurs at a higher frequency than on the package insert; or (2) meets the

criteria for a serious adverse event. The collection of AEs information will begin on the first day of initiation of therapy.

- Cohorts 1 and 2: Because grade 3 and 4 laboratory abnormalities which do not result in any clinical action frequently occur during h-ATG administration, only those events that result in a clinical action (i.e., dose reduction/discontinuation, prolongation of hospitalization, etc.) will be recorded in the database during the first week of h-ATG treatment.
- Cohort 3 the Extension Cohort, and Laboratory Exploratory Cohort: Because grade 3 and 4 adverse events which do not result in any clinical action frequently occur during h-ATG administration, only those events that result in a clinical action (i.e., dose reduction/discontinuation, prolongation of hospitalization, etc.) will only be recorded in the database from the start of h-ATG to 14 days post-treatment. The exception to this will be if the event, which did not result in a clinical action, can be associated with both eltrombopag and h-ATG, and the event attribution cannot be assigned with a high level of certainty to only h-ATG, then these events will be recorded in the database and reported to the IRB per Policy 801.
- Cohort 3, the Extension Cohort, and Laboratory Exploratory Cohort: Grade 3 and 4 LFTs will be recorded in the medical record, and only recorded in the database as adverse events from the start of h-ATG to 14 days post treatment.
- All grade 1 events listed as expected in the protocol, consent forms, or other applicable protocol documentation.

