Transient hepatotoxicity is an expected and common side effect of h-ATG that occurs during the first 14 days following the start of h-ATG administration. In the event of an increase in the ALT level to > 6 times the ULN during Days 1 – Days 14, eltrombopag will be held until ALT is < 5 times the ULN and then resumed at the same dose. If the ALT rises to > 6 times ULN after resuming eltrombopag (and is not attributable to other inciting factors such as serum sickness, sepsis, or azole antifungal agents) then the ALT will be monitored at least every 3-4 days. If the ALT remains > 6 times the ULN on repeat blood tests, eltrombopag will be stopped until the ALT is < 5 times the ULN. Then eltrombopag will be restarted at a dose level that is 25 mg/day lower than the prior dose. If liver test abnormalities return to an ALT of > 6 times ULN on this reduced dose, the eltrombopag dose will be reduced by 25 mg/day until there is reduction of ULN to < 5 ULN.

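### For Cohort 3 and the two later cohorts, the grade 3-4 LFT rule most naturally stops AE recording of non-serious liver events at about day 14-18, while eltrombopag and the primary safety endpoint run to 6 months

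*Combined protocol and SAP*

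**What the plan says.** Section 10.2.3 sets a general rule and then a list of exclusions.

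- **General rule.** Non-hematologic laboratory changes that "result in a progression to a grade 3 or 4 laboratory toxicity" are among the findings used to evaluate safety. Database recording starts with study drug and "will continue for 30 days after the 6 month landmark visit", or for 30 days after treatment stops if that comes sooner.
- **Lead-in to the exclusions.** It states that "the following non-hematologic AEs will be captured only in the source documents and will not be recorded in the database".
- **Cohorts 1 and 2.** Of the grade 3-4 laboratory abnormalities, only those that led to a clinical action "will be recorded in the database during the first week of h-ATG treatment". There is no separate LFT item.
- **Cohort 3 and the two later cohorts, all grade 3-4 events.** Only events with a clinical action are recorded, from the start of h-ATG to 14 days post-treatment. The exception is an event that could be due to both drugs and for which "the event attribution cannot be assigned with a high level of certainty to only h-ATG".
- **Cohort 3 and the two later cohorts, LFTs.** Grade 3-4 LFTs go in the medical record and are "only recorded in the database as adverse events from the start of h-ATG to 14 days post treatment".

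Elsewhere, section 9.3 makes the toxicity profile over 6 months the primary safety endpoint. Section 9.1 continues eltrombopag in Cohort 3 to the 6-month visit, and section 3 gives the Extension and Laboratory cohorts the same schedule. Section 5.5.2 describes h-ATG liver toxicity as transient and as something "that occurs during the first 14 days following the start of h-ATG administration".

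**The concern.** The LFT item switches AE recording on while h-ATG is the expected cause of liver abnormalities, and off once that explanation has passed. Eltrombopag then continues for months. A non-serious grade 3 or 4 transaminase rise at month 2 or 4 would have no AE entry and no attribution, and would not reach the toxicity tables. Section 11.4.3 places the isolated cases of severe liver injury seen in eltrombopag trials at about three months after the drug was started, well beyond day 18.

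At stake is the completeness of the primary safety endpoint in Cohort 3. Sections 2.9.2 and 3 explain that Cohorts 1 and 2 delayed eltrombopag to day 14 because of liver toxicity, and Cohort 3 removes that delay. A liver profile that stops after two to three weeks is not the 6-month profile that section 9.3 promises.

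**Working it through.** The plan gives no figure to reproduce, so the check is day arithmetic and a comparison of the texts.

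**Inputs**
- h-ATG: 4 consecutive days, days 1-4 (section 5.1).
- Eltrombopag in these cohorts: day 1 to the 6-month visit (sections 3 and 9.1).
- General AE recording: to 30 days after the 6-month visit (section 10.2.3).
- Assumption: 6 months = 183 days. The general period then ends at 183 + 30 = day 213.
- Planned subjects (title page): Cohort 3, 31; Extension, 87; Laboratory, 25.

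**If treatment means h-ATG**
- Cut-off: day 14 counted from the start of h-ATG, or 4 + 14 = day 18 counted from the last dose.
- Eltrombopag days with AE recording of these LFTs: 14/183 = 7.7% to 18/183 = 9.8%.
- Eltrombopag days without it: 183 - 18 = 165 (90.2%) to 183 - 14 = 169 (92.3%).
- Days of the general recording period without it: 213 - 18 = 195 (91.5%) to 213 - 14 = 199 (93.4%).

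This is the most natural reading. The window opens with h-ATG, the preceding item uses the same phrase for an h-ATG exemption, and 14 days matches the period in section 5.5.2.

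**If treatment means eltrombopag**
- Cut-off: 183 + 14 = day 197, so there is no gap while on drug.
- Shortfall against the general period: 213 - 197 = 16 days.
- The preceding item would have to be read the same way. Its exemption for grade 3-4 events without clinical action, justified there by h-ATG administration, would then last more than 6 months.

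**If the wording is a slip for the reverse** (medical record only during the window, database afterwards)
- The gap is the first 14-18 days (7.7-9.8% of 183).
- LFTs that cause eltrombopag to be held in days 1-14 under section 5.5.2 would go unrecorded, although the preceding item records events with a clinical action. The documents do not say that this was meant.

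**Who is affected**
- Primary safety endpoint: 31 planned subjects in Cohort 3.
- Descriptive safety record only: 87 + 25 = 112. Section 9.1 keeps the Extension Cohort out of the Cohort 3 primary analysis, and section 2.9.4 gives the Laboratory cohort a laboratory purpose.

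No reading agrees with the general rule, the preceding item and the 6-month endpoint together.

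**The case against.** The strongest defence has four parts.

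1. **The list holds partial exclusions.** Several items under the lead-in also say what is recorded, so the LFT item can be read as source documents only, except within the window. This stands: the clash with the lead-in is loose drafting shared by the list. But that reading confirms the early cut-off.
2. **The window captures what is new in Cohort 3.** The novelty is overlap of eltrombopag with h-ATG, and the item records grade 3-4 LFTs in that period without requiring a clinical action. From day 14 to month 6, Cohort 3 receives eltrombopag as Cohort 1 does. This also stands, and the item may have been a deliberate inclusion. It does not shorten the safety endpoint, which covers 6 months in every cohort.
3. **Liver data survive.** Serious events are recorded throughout the study (section 10.2.4). AST, ALT, ALP and bilirubin are entered to 6 months (section 6.3), with NIH results imported electronically and home values keyed in (section 9.7). This stands. What is lost is the AE record and attribution of non-serious events.
4. **Other exclusions overlap.** For all cohorts, "any observed or volunteered adverse events that are listed on the package insert will not be captured in the research database unless" they are more severe or more frequent than labelled, or serious. Section 11.4.3 lists increased transaminases at 12%, so some of these events may drop out anyway. This stands, and it is why the added loss cannot be sized.

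A reader might go further and infer that all AE recording stops, that the stopping rule is blind after day 18, or that a planned liver comparison of Cohort 3 with Cohorts 1 and 2 is biased. The documents support none of these. The item concerns grade 3-4 LFTs only. Section 9.5 counts any grade IV toxicity probably or definitely related to eltrombopag, as a serious event. Section 9.2 compares each cohort separately with historical data and specifies no between-cohort LFT comparison. The recording rules of the earlier studies named in section 9.4 are not given, so bias there cannot be shown either.

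**Conclusion.** The rule is wrong as written and should be fixed. On its most natural reading it ends AE recording and attribution of non-serious grade 3-4 LFTs at about day 14-18, against a general period of about 213 days and an endpoint of 6 months. The eltrombopag reading removes the on-drug gap but leaves the 16-day shortfall and makes the neighbouring exemption implausibly long.

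The size can be given in days and subjects but not in events: the documents give no rate of non-serious grade 3-4 LFTs in this trial, and the package-insert exclusion overlaps. The conclusion rests on reading *post treatment* as h-ATG and on taking 6 months as 183 days. It is a gap in AE coding and attribution that bears on the primary safety endpoint in 31 subjects. It is not a loss of liver data.

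**What to change.** 1. **Use the stored values.** Derive the 6-month liver toxicity tables for all cohorts by programmed CTCAE grading of the recorded ALT, AST, ALP and bilirubin values. Review the attribution of any grade IV value found after the h-ATG window against section 9.5. This step matters most. Section 2.9.4 reports 178 of 182 subjects already accrued, and section 2.9.3 says that the Extension Cohort opened after Cohort 3 had completed enrolment, so new wording helps mainly the 25 Laboratory subjects.
2. **Reconcile the text.** State that in these three cohorts grade 3-4 LFTs are recorded as AEs, with attribution, to 30 days after the 6-month visit. Within the h-ATG window, apply only the existing exemption for events without clinical action and its existing exception. Define *post treatment* by study day in both items.

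The cost is one reworded item, one definition, a grading program and attribution review of a limited set of events. Section 6.3 provides for liver values only to 6 months, so grading them serves the primary endpoint but does not fill the final 30 days. The package-insert exclusion is a separate matter and need not change for this fix.

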10.2.4 Serious Adverse Events Characterization

Serious adverse events will be attributed as definitely (clearly related to the research), probably (likely related to the research), possibly (may be related to the research), unlikely (doubtfully related to the research) and unrelated (clear not related to the research).

TRSAEs are those attributed as definitely or probably. As detailed in section 9.5 stopping rules, TRSAE that will be monitored and considered for early stopping the study according to statistically determined criteria include Death and any grade IV toxicity considered to be probably or definitely related to study medication.

Hospitalizations for administrative issues (e.g., to receive a transfusion after hours) or movement to the ICU for routine monitoring per administrative requirements or nosocomial isolation will be captured in the database.

Duration of Serious Adverse Event collecting and reporting: The collection or recording of SAEs in the database will begin on the first day of initiation of the study drug and will continue as long as the subject is on study.

Serious adverse event recording for events that are unexpected and/or definitely, probably or possibly related to the study drug will continue as long as the subject remains on study.

10.2.5.1 NIH Intramural IRB and NHLBI Clinical Director (CD) Reporting

Expedited Reporting

Events requiring expedited reporting will be submitted to the IRB per HRPP Policy 801 “Reporting Research Events”.

Reports to the IRB at the time of continuing review:

The PI or designee will refer to HRPP Policy 801 “Reporting Research Events” to determine IRB reporting requirements.

Reports to the CD:

The PI or designee will refer to NHLBI DIR guidelines to determine CD reporting requirements. In addition, the following commonly occurring disease specific Serious Adverse Events (SAEs) will be captured in the database but are not required to be reported to the CD per NHLBI guidelines:

- Neutropenic fever
- Minimal bleeding (such as nose bleed or menorrhagia)
- Transfusion reactions to red blood cells and/or platelets

10.2.5.2 NHLBI DSMB Reporting

Reports of serious adverse events that are unexpected and suspected will also be forwarded as soon as possible, but no later than seven (7) days in the case of death or life-threatening serious adverse events or within fifteen (15) days after the occurrence of all other forms of serious adverse events to the Data and Safety Monitoring Board (DSMB). All events will be included in DSMB reports for review by the DSMB.

10.2.5.3 Sponsor and FDA Reporting

IND: 104877

IND Sponsor Representative: [name]

The PI will report SAEs to the Sponsor according to the requirements of 21 CFR 312.64(b) and as agreed upon with the sponsor. The Sponsor (or designee) will determine the reportability of the event to the FDA and IND safety report will be submitted to the FDA as required.

IND Safety Reports to the FDA (Refer to 21 CFR 312.32)

The sponsor must notify the FDA in an IND safety report of potential serious risks, from clinical trials or any other source, as soon as possible, but in no case later than 15 calendar days after the sponsor determines that the information qualifies for reporting. The sponsor must also notify FDA of any unexpected fatal or life-threatening suspected adverse reaction as soon as possible but in no case later than 7 calendar days after the sponsor's initial receipt of the information.

15-day reporting

The sponsor must report any suspected adverse reaction that is both serious and unexpected. The sponsor must report an adverse event as a suspected adverse reaction only if there is evidence to suggest a causal relationship between the drug and the adverse event, such as:

- A single occurrence of an event that is uncommon and known to be strongly associated with drug exposure (e.g., angioedema, hepatic injury, Stevens-Johnson Syndrome);
- One or more occurrences of an event that is not commonly associated with drug exposure, but is otherwise uncommon in the population exposed to the drug (e.g., tendon rupture);

An aggregate analysis of specific events observed in a clinical trial (such as known consequences of the underlying disease or condition under investigation or other events that commonly occur in the study population independent of drug therapy) that indicates those events occur more frequently in the drug treatment group than in a concurrent or historical control group

The sponsor must submit each IND safety report in a narrative format or on FDA Form 3500A.

FDA contact:

CDER Therapeutic Biological Products Document Room
Center for Drug Evaluation and Research, Food and Drug Administration
[name]
[contact]

A summary of all SAEs, non-serious AEs, and other events will be recorded and submitted to the Sponsor and FDA in annual progress reports (21 CFR 312.64(b)).

